6.2 PREPARATION/HANDLING/STORAGE/ACCOUNTABILITY

6.2.1 ACQUISITION AND ACCOUNTABILITY

We will obtain ripasudil 0.4% from Mimaki Family Pharmacy, Osaka, Japan, and Japan Health (bio-japan), Japan under IND #154317. Partner pharmacies will store and compound study medications: Rancho Park Compounding Pharmacy (for Stanford University, UC Davis, and OHSU); Penn Investigational Drug Services (for University of Pennsylvania); and Dartmouth Health Investigational Drug Services (for Dartmouth Hitchcock Medical Center). Medications and masked placebos will be purchased by the study and distributed to each enrolled patient individually by the partner pharmacies.

6.2.2 FORMULATION, APPEARANCE, PACKAGING, AND LABELING

Transfer of topical study medication or placebo to an identical bottle by the compounding pharmacy will ensure patient and physician remain masked to treatment arm.

6.2.3 PRODUCT STORAGE AND STABILITY

All study medications should be stored at 15-25°C and should be protected from sunlight. Expiration dates will be clearly labeled. The shelf life for ripasudil will be 97 days. For study drug accountability see Appendix Study Drug Accountability Log. For study drug preparation, study drug storage, and study drug distribution see Appendix RP SOP 9.00 V 1.0, RP SOP 3.15 V 1.1, RP SOP 3.10 V 1.2, RP SOP 3.20 V 1.5.

6.2.4 PREPARATION

All preparation will be performed by the partner pharmacies and dispensed directly to the patient.

6.2.5 STUDY MEDICATION TRACKING

Once it has been determined that a patient is eligible for the study, their name and mailing address will be entered in REDCap, along with a Baseline Pharmacy Information Form which provides the partner pharmacy with information about allergies and current medications. All study drug tracking will occur within the REDCap database. Randomization into the study will trigger an email notification to the UCSF Study Coordinator, who will communicate with the respective partner pharmacy. The partner pharmacy will be informed of 1) which study arm the patient has been randomized to, and 2) the surgery date. The UCSF Study Coordinator will enter the date and time communication with pharmacy personnel into the REDCap database. All study medication will be dispensed directly to the patient from the corresponding partner pharmacy.

Several days prior to surgery, the pharmacy will prepare the study medication and log into REDCap to enter information about study drug shipment: date and time shipped; lot number; and FedEx tracking info. The site study coordinator or treating physician will contact the patient to ensure receipt of the study drug (Y/N; date received) and review instructions. This will also be logged into the REDCap database. At each study visit, the patient will be asked to bring all bottles of study related medication to review at follow up visits. At the 3- month study visit the study drug bottles will be collected by the study coordinator and any remaining medication will be pulled from the dropper with a syringe to measure the remaining volume. The study coordinator will log the volume in REDCap. Medication adherence questions will be included in the follow-up form at the 3-month study visit.

6.2.6 STUDY MEDICATION PREPARATION

Please see Rancho Park Standard Operating Procedures for full details. Ripasudil will be received and stored according to the conditions and temperature requirements set by the manufacturer. Ripasudil, a commercially available sterile

DETECT

Version 5.0
21 March 2023

preparation, will be repackaged (6.5mL Ripasudil into a 10mL sterile dropper) using simple one step transfer of the product with no additional manipulation. Beyond Use Date (BUD) stability testing has been approved for 120 days.

The repackaged sterile investigational product will be packaged in an identical container as placebo which will be a commercially available artificial tear. Pharmacies will not repackage the artificial tears but will re-label the outside of the bottle following requirements of California Code, Business and Professions Code – BPC 4076 to match the repackaged Ripasudil so that they have identical appearances. The pharmacist will perform final quality control of the product before it is released to the shipping department.

6.2.7 STUDY MEDICATION DISTRIBUTION

Once the study drug has been prepared, it will be released to the shipping department where it will be shipped directly to the patient. Validated shipping methods per storage conditions and temperature requirements will be ensured during shipment. Medications and masked placebos will be provided to each patient individually from the partner pharmacy.

In addition to ripasudil/placebo, DETECT II patients will receive a second study medication. Initially all DETECT II patients will receive dexamethasone. The enrolling physician will prescribe 10mL of dexamethasone eye drops to begin post-operatively. After 30 days, partner pharmacies will provide the second study medication. Those randomized to DSO will switch to a placebo and those randomized to DMEK will continue on dexamethasone. Medications and masked placebos will be purchased by the study and distributed to each enrolled patient individually by the partner pharmacies.

6.2.8 CONCOMITANT MEDICATIONS

There are no known drug interactions with Ripasudil. There are no known side effects when taking Ripasudil with two or more medications concurrently.

6.3 MEASURES TO MINIMIZE BIAS: RANDOMIZATION AND BLINDING

For both trials, patients will be randomized by the eye bank 1-3 weeks prior to surgery. In DETECT I, each study eye will be randomly assigned separately to the two treatment groups (DMEK/UT-DSAEK, ripasudil/placebo). Block randomization will be performed using a computer program (Statistical package R; Version 3.6; R Foundation for Statistical Computing, Vienna Austria) by the data coordinating center. Once an eye is enrolled in the study, the study coordinator will assign the study participant's eye an ID (alpha-numeric code).

Prior to surgery, the eye bank will assign the study participant corneal tissue. Once the corneal tissue has been assigned, the eye bank will look at the treatment assignment with regard to surgical treatment and prepare the tissue accordingly. For DETECT II, the tissue will be randomized and assigned to the patient if the patient is randomized to DMEK. The eye bank will also inform the surgeon of the study participant's randomization assignment with regard to type of surgery.

The eye bank will randomize tissue using the Microsoft Excel RANDBETWEEN formula. A new file will be created for each study eye and uploaded to REDCap. The eye bank will highlight the randomized tissue in the Excel file (the randomization runs every time the file is opened), so the original randomization is documented. If tissue does not pass post-processing evaluation, becomes ineligible for some other reason, or it does not meet study parameters, e.g. >90 microns, the randomization process will be repeated, the same Excel file can be used.

Once the study eye has been assigned a study participant ID and randomized to treatment group they will be included in the intention to treat analysis. (Note: See **MOP – Section 4.3** for full donor tissue procurement and assignment information).

All study participants will be masked to their intervention. The refractionist performing the BSCVA will also be masked. Due to the nature of the intervention, the surgeon and technician performing study visit endothelial cell counts and

DETECT

Version 5.0
21 March 2023

other imaging will not be masked as to surgery type (but will be masked as to study medication); however, image graders at the Proctor Reading Center and CIARC will be masked. Eye bank personnel will not be given any identifying information.

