2.3 RISK/BENEFIT ASSESSMENT

2.3.1 KNOWN POTENTIAL RISKS

Study participants will not have any increased risk or cost for participating in this study. Participants in the study have the same risks as those undergoing corneal transplantation in other settings. Many of the risks in this study are inherent risks of corneal transplantation; thus, there is no known increased risk associated with participation in this study.

As with any surgery, there are risks associated with these surgeries, and both surgeries have similar risks. There is a risk of infection or bleeding which could result in vision loss. There may be damage to the tissue graft during tissue preparation, and the tissue graft can fail to attach to the cornea; thus, there may be a need for repeat air injection.

Below, the other risks associated with each type of surgery are listed:

- UT-DSAEK: There may be slightly decreased vision after surgery compared to DMEK, although this is unknown. The healing process may also be slower. Some think there is an increased risk of rejection compared to DMEK, although this is also unknown. There is a small risk of intraocular pressure rise with painful glaucoma attack in the immediate postoperative period that can cause permanent glaucomatous optic nerve damage resulting in visual field deficits.
- DMEK: There may be increased risk of tissue loss, repeat air injection, detachment of the tissue graft to the cornea compared with UT-DSAEK. There may be higher costs associated with this surgery, although these additional costs will be covered by insurance. There is a small risk of intraocular pressure rise with painful glaucoma attack in the immediate postoperative period that can cause permanent glaucomatous optic nerve damage resulting in visual field deficits.
- DSO: The healing process may be slower than after DMEK or UT-DSAEK. There is a risk that a second surgical for endothelial keratoplasty would be required. Topical ripasudil may cause a local allergic reaction, eye redness or irritation, or upset stomach.

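### DETECT I replacement grafts needed after processing are redrawn with the surgical arm known, in a self-recalculating spreadsheet whose only stated record of the draw is a manual highlight

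*Protocol*

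**What the plan says.** Section 6.3 of the protocol describes two separate random steps. Patient treatment is block-randomized from a list generated in R by the data coordinating center. Donor tissue is drawn by the eye bank: "The eye bank will randomize tissue using the Microsoft Excel RANDBETWEEN formula".

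In DETECT I the order is fixed: "Once the corneal tissue has been assigned, the eye bank will look at the treatment assignment with regard to surgical treatment and prepare the tissue" in line with that assignment. In DETECT II the tissue draw follows the arm: "For DETECT II, the tissue will be randomized and assigned to the patient if the patient is randomized to DMEK".

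One file is made per study eye and uploaded to REDCap. On the record of the draw, 6.3 says: "The eye bank will highlight the randomized tissue in the Excel file (the randomization runs every time the file is opened". It presents the highlight as documenting the original draw.

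Replacement is called for when tissue fails its evaluation after processing, becomes ineligible for any other reason, or falls outside study parameters, with thickness over 90 microns as the example. Then "the randomization process will be repeated, the same Excel file can be used". Section 6.3 refers to MOP section 4.3, which is not at hand, for the full tissue procedure.

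**The concern.** Drawing tissue before opening the surgical assignment keeps the choice of donor independent of the arm. The replacement rule gives that up for any graft that fails after preparation, because the eye bank has by then seen the arm. The tool adds to the problem: each opening of the file yields another donor, reuse of the file is allowed, and 6.3 does not say how a redraw, its reason or the rejected tissue is recorded.

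The comparison at stake is UT-DSAEK versus DMEK. It is a primary comparison for 12-month BSCVA, a key secondary comparison for 12-month ECL (9.4.3), and it bears on graft failure. The models in 9.4.2 adjust for baseline BSCVA or for eye-bank ECD. They contain no other donor feature, such as donor age or preservation time. Intention-to-treat analysis does not help, because the question is which graft the eye receives.

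**Working it through.** The protocol gives no figure for the tissue draw, so none can be reproduced. The check is one of sequence, followed by a scale calculation on assumed inputs.

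**Sequence in DETECT I**

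1. Tissue is drawn and assigned, with the surgical arm not yet viewed (6.3).
2. The eye bank views the surgical assignment and prepares the tissue for it (6.3). Preparation differs by arm: a microkeratome cut to about 60-90 microns for UT-DSAEK; peeling, punching and pre-loading for DMEK (6.1.1).
3. Failed post-processing evaluation, or a cut thicker than 90 microns, can be known only after step 2. A redraw for either reason is therefore made with the arm known.
4. Tissue that becomes ineligible for another reason before step 2 can still be redrawn with the arm unseen. Only part of all replacements is unconcealed.
5. The formula recalculates at each opening, so the stored file cannot confirm that the highlighted tissue is the one first drawn. For a redraw, 6.3 states no record at all.

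**Number of grafts.** The replacement rate is not given. Assuming 5-15%, 160 × 0.05 = 8 to 160 × 0.15 = 24 grafts in DETECT I would be replaced. By step 4 this is an upper limit for draws made with the arm known.

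**Scale if the redraw were misused.** Inputs from the DETECT-TES table in 9.4.5: pre-processing donor cell count 2792 (SD 210) and 2797 (SD 222) cells/mm². Average SD = (210 + 222)/2 = 216; average count about 2795. Suppose the best of k donors is taken for a share r of grafts in one arm only (assumption). Then

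shift = r × E[maximum of k standard normal values] × 216,

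where the expected maximum is 0.565 for k = 2 and 0.847 for k = 3.

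| r (assumed) | best of 2, cells/mm² | best of 3, cells/mm² |
|---|---|---|
| 5% | 6.1 | 9.1 |
| 10% | 12.2 | 18.3 |
| 20% | 24.4 | 36.6 |
| 30% | 36.6 | 54.9 |

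For comparison, the 7-point ECL difference in 9.2 is 0.07 × 2795 = 196 cells/mm². Best of two in 10% of one arm is 12.2/196 = 6% of that; the most extreme cell is 54.9/196 = 28%. These shifts are before adjustment for eye-bank ECD, which would take out much of a difference in starting count.

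**Scale for other donor features.** If arm-known replacements differed from other grafts by 5 points of ECL and made up 15% of one arm and 5% of the other (all assumed, with no basis in the document), the contrast would move by (0.15 − 0.05) × 5 = 0.5 points, against the planned 7. For BSCVA the protocol gives nothing from which to size an effect.

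**The case against.** A redraw done as written is still random; bias requires someone to reopen the file and choose. There is also a trail: one file per eye in REDCap, with the drawn tissue highlighted, and the protocol openly states that the formula recalculates. MOP section 4.3 may hold rules on logging and discards. Section 9.4.5 plans to report donor age, sex, preservation and surgery times and cell counts, so marked selection on those features could show. All of this stands, and it limits the point. It does not remove it: the arm-known redraw, the recalculating file and its reuse are all written into the protocol, and a highlight cannot be checked against a number that has since changed.

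A reader might infer more than the text supports:

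- *Replacement rules differ by arm.* They do not. One rule covers all tissue; only the over-90-micron trigger is confined to UT-DSAEK.
- *Redraws will be more frequent in one arm.* This is unknown. The thickness trigger adds redraws in UT-DSAEK. For DMEK, section 2.3.1 says "There may be increased risk of tissue loss", but as a possibility within a list of patient risks, and the same section names damage during preparation as a risk of both surgeries. The two could offset each other.
- *The primary ECL comparison is affected.* Section 6.3 has the eye bank view the surgical assignment only, so ripasudil versus placebo is not shown to be exposed.
- *DETECT II is biased.* Only DMEK receives a graft there, so there is no between-arm tissue comparison to distort.
- *Patient allocation is unconcealed.* The treatment list is separate from the tissue draw and comes from the data coordinating center.

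**Conclusion.** The point holds in a limited form. In DETECT I, a replacement needed because prepared tissue failed evaluation or was too thick is drawn with the surgical arm known, by a method whose result cannot be verified later. This is a weakness of concealment and documentation, not evidence of bias. It is confined to UT-DSAEK versus DMEK: 12-month BSCVA, key secondary ECL and graft failure.

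Any effect is probably small: about 6 to 55 cells/mm² of donor count before adjustment, or 0.5 points of ECL, under assumptions that the document neither supports nor contradicts. The replacement rate, the size of the tissue pool and the timing of the REDCap upload are not given. The case for acting is that the remedy is cheap and that draws overwritten by recalculation cannot be recovered later.

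**What to change.** In section 6.3 (and the MOP), replace the repeated draw with a ranking fixed in advance:

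- Before the surgical assignment is opened, rank all eligible tissues for that eye once. Save the ranks as static values, or take them from a seeded list held by the data coordinating center, and upload the locked file to REDCap.
- If a tissue fails, use the next available rank.
- If the list is exhausted or the remaining tissue has expired, make a new time-stamped, locked draw, ideally by the data coordinating center.
- Log every discarded tissue with its reason.
- Report replacements and donor characteristics by surgical arm.

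The cost is a slightly longer eye-bank worksheet and a few sentences of text, with no extra visits. A frozen list will sometimes run out as the donor pool turns over (death to surgery averaged about 6 days in DETECT-TES, per 9.4.5), so an occasional fresh draw with the arm known will remain. It would then be time-stamped and open to checking.

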6.4 STUDY INTERVENTION COMPLIANCE

We will have several measures in place to assess compliance with medications. We will have outpatient medication logs to track compliance and missed doses, to be filled out by the patient. At follow-up visits, patients will be asked to bring their used medication bottles.

6.5 CONCOMITANT THERAPY

The masked treating physician will be allowed add or change any therapy deemed necessary, including surgery. These changes will be recorded and reported.

6.5.1 RESCUE MEDICINE

The masked treating physician will be allowed to add or change any therapy deemed necessary, including surgery. These changes will be recorded and reported.

7 STUDY INTERVENTION DISCONTINUATION AND PARTICIPANT DISCONTINUATION/WITHDRAWAL

7.1 DISCONTINUATION OF STUDY INTERVENTION

Discontinuation from assigned study intervention does not mean discontinuation from the study, and remaining study procedures should be completed as indicated by the study protocol. If a clinically significant finding is identified (including, but not limited to changes from baseline) after enrollment, the investigator or qualified designee will determine if any change in participant management is needed. Any new clinically relevant finding will be reported as an adverse event (AE).

The data to be collected at the time of study intervention discontinuation will include the following:

- Reason for study intervention discontinuation
- New prescribed treatment

7.2 PARTICIPANT DISCONTINUATION/WITHDRAWAL FROM THE STUDY

Participants are free to withdraw from participation in the study at any time upon request. The reason for participant discontinuation or withdrawal from the study will be recorded on the final status eye form, which will be filled out at time of participant withdrawal (instead of at study completion) for patients withdrawing from the study. Subjects who sign the informed consent form and are randomized but do not receive the study intervention may not be replaced and will be included in the intent to treat analysis. Subjects who sign the informed consent form, and are randomized and receive the study intervention, and subsequently withdraw, or are withdrawn or discontinued from the study, will not be replaced and will be included in the primary analysis.

7.3 LOST TO FOLLOW-UP

All efforts will be made to prevent loss to follow-up during the trial. We will assess whether missing outcomes are differential by arm. If we find differential loss to follow-up, or if primary outcomes are missing in >15% of eyes, we will conduct a sensitivity analysis that uses inverse probability of censoring weights to correct for potential bias due to potentially informative censoring, following best practice guidelines for the prevention and treatment of missing outcomes in clinical trials.⁴⁶⁻⁴⁸

DETECT

Version 5.0
21 March 2023

8 STUDY ASSESSMENTS AND PROCEDURES

8.1 EFFICACY ASSESSMENTS

The following masked efficacy assessments will be performed:

- **Visual acuity assessment.** BSCVA/ETDRS/MRx will be used to assess visual acuity. Visual acuity will be assessed only by a trained, masked optometrist to ensure proper procedures are followed across sites. See **MOP – Section 4.4** for the visual acuity protocol.
- **Slit lamp examination.** Performed by the treating physician.
- **Imaging assessments.** Non-contact imaging will be performed with Pentacam topography and densitometry, clinical photography, and endothelial imaging. Historical tests/images within one month prior to enrollment will be acceptable if treating physician deems results representative of the current health of the eye. See **MOP – Section 4.5 and CIARC Appendix** for detailed descriptions of imaging procedures. Performed by trained study staff.
- **Visual function questionnaire (VFQ).** The National Eye Institute Visual Function Questionnaire (NEI-VFQ), a validated questionnaire to evaluate the effect of vision on the patient's quality of life, will be administered. Performed by trained study staff.

Please see the SoA in **Section 1.3** of this protocol for a detailed schedule of all study activities.

Visual acuity assessment, slit lamp examination, and Pentacam imaging will be performed during the screening process. These are standard of care procedures that the patient would receive even if they were not being screened for the study. The masked treating physician may use the results of these assessments to change the participant's treatment in any way they deem necessary.

8.2 SAFETY AND OTHER ASSESSMENTS

The following assessments will be administered to monitor patient safety:

- **Interval history from the patient** to ask about side effects, etc.
- **Visual acuity assessment.**
- **Intraocular pressure.**
- **Slit lamp exam to identify complications.** Ongoing AEs and SAEs will be followed until resolved.
- **Assessment of study intervention adherence.** See Study Intervention Compliance, **Section 6.4**.

8.3 ADVERSE EVENTS AND SERIOUS ADVERSE EVENTS

8.3.1 DEFINITION OF ADVERSE EVENTS (AE)

Adverse event means any untoward medical occurrence associated with the use of an intervention in humans, whether or not considered intervention-related (21 CFR 312.32 (a)).

8.3.2 DEFINITION OF SERIOUS ADVERSE EVENTS (SAE)

An adverse event (AE) or suspected adverse reaction is considered "serious" if, in the view of either the investigator or sponsor, it results in any of the following outcomes: death, a life-threatening adverse event, inpatient hospitalization or prolongation of existing hospitalization, a persistent or significant incapacity or substantial disruption of the ability to conduct normal life functions, or a congenital anomaly/birth defect. Important medical events that may not result in death, be life-threatening, or require hospitalization may be considered serious when, based upon appropriate medical judgment, they may jeopardize the participant and may require medical or surgical intervention to prevent one of the outcomes listed in this definition.

DETECT

Version 5.0
21 March 2023

